The primary objective of this study is to examine in a double blinded and randomized trial the efficacy of Recombinant Human lactoferrin (rhLF) in reducing chronic inflammation as measured by IL-6 and sTNFR1 in the bloodstream. Secondary objectives include assessing the efficacy of rhlactoferrin (rhLF) in attenuating cognitive decline as measured by the Digit Symbol Substitution Test and Trail Making Test, as well as improving physical mobility as measured by performance on 4 meter and six-minute walk tests. The tertiary objective of this study is to gather information about the tolerability of and adherence to oral rhlactoferrin (rhLF) among older adults with CI over a three-month period.

3. Background

Chronic Inflammation and Biological Mediators:

Chronic inflammation (CI) as defined by chronic elevation in serum inflammatory measures is a known risk factor for a host of adverse health outcomes in older adults (3;17;18). The etiology of CI is complex with increased chronic disease burden, fat mass, free radicals, and senescent cells, dysfunctional mitochondria, altered microbiome, and decreased GI tract barrier function all potentially contributing (19-25). Dozens of population studies have detailed significant associations between pro-inflammatory measures and functional and mobility decline, frailty, worsening chronic illness, cognitive decline, mortality and reduced gait speed (1;2;26;27;28). Although these relationships were often considered to be epidemiological phenomena rather than causal, evidence suggests that chronic exposure to some inflammatory mediators can lead directly to molecular and tissue changes that contribute to the observed adverse outcomes (29;30-34). Specifically, evidence suggests that IL-6, sTNFR1 and other molecules directly and negatively impact skeletal muscle and neurologic tissue through impairment of satellite cells, through the triggering of cell death pathways, and through other mechanisms (35-44). Figure 1 provides a conceptual overview for a biologically plausible pathway between CI and health-related declines; lactoferrin is hypothesized to impact inflammatory mediators and their downstream effects.

Chronic Inflammation and Cognitive Decline:

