Most prior studies linking CI to adverse health in older adults have relied on single serum-based biomarkers such as IL6 or C-reactive protein (CRP). Studies have emerged that demonstrate that elevations in ≥2 inflammatory markers are more strongly associated with adverse outcomes (53-57). Approaches to aggregate markers can be categorized into “unsupervised” and “supervised”, with unsupervised aggregation being a summary of markers obtained based only on their joint distribution, e.g. by z-scores, principal component analysis or exploratory factor analysis (58;60) and supervised aggregation also considering biological understanding, or externally validating response (e.g., mortality(26)) for an “optimally” predicting response. Our group has made key contributions to work on supervised aggregation of inflammatory markers; including the first study applying latent variable (LV) modeling to summarize markers in accordance with biology understanding (61). Subsequently, we demonstrated that an inflammatory index (IIS) combining serum levels of IL6 and sTNFR1 provided superior prediction of 10-year mortality in the Cardiovascular Health Study (N=5,177) (26) over many other cytokines. As rationale for the use of these measures for diagnosis of CI in this project over other markers, we performed additional analyses (table 1) using the likelihood ratio test that shows that IL-6, TNFR1, and combined measure IIS are superior predictors of gait speed declines over 10 years when compared to CRP and interleukin 1 receptor antagonist (IL1RA). The cutoff

point for the study inclusion criteria for IL6 was identified based on a published threshold serum value above which adverse outcomes are much more common; the value for sTNFR1 was identified using a loess curve generated from data analyzed from the Cardiovascular Health Study (17;18;26). This background research provides strong rationale for the use of these measures to identify CI and to monitor treatment efficacy of lactoferrin on CI.

4. Study Procedures

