Measurements Performed at Visits:

Phlebotomy (primary outcome measure): Primary outcome will be serum IL-6 and sTNFR1 as measured by ELISA as previously performed in the PI's laboratory by an experienced laboratory technician. Blood will also be measured for CBC w/Diff, and CMP, these measures will be made from blood drawn at SV, ABT, BV, FU1, FU3 and FU6. Rationale for the choice of these measures are provided above in the background section.

A Physical Exam will be taken at SV. A Medical History will be taken at SV and a Brief Medical History Review at BV and all subsequent FUV. These are to assess eligibility or contraindicate the intervention, detect new conditions or complications and other safety signals, and to measure important covariates (i.e. demographics, past medical history, current activity levels, routine medication, and vitamin use).

4 meter walk: Speed of walking at usual pace over 4 meters will be measured at the SV, BV, FU3, and FU6.

Six-minute walk: This is performed at the BV, FU3, and FU6 by having the participant walk along a straight hallway for six minutes and measuring the distance walked and the sensation of leg fatigue and dyspnea. The participant is given scripted prompts at one-minute intervals, but the test is largely self-directed and self-limited.

Short Physical Performance Battery (SPPB): This is an assessment of lower extremity functioning comprised of gait speed, balance, and leg strength and is performed at the BV and FU6. As part of the SPPB, participants will complete a balance test assessing their ability to stand without assistance and a chair stand test.

Cognitive Function Measures: The Digit Symbol Substitution Test (DSST) is a sensitive measure in cognitively normal older adults. It measures attentional control and switching, and more broadly executive processes and thus is not sensitive to impairment in particular brain regions. It is a highly precise measure across the range from cognitively normal to mildly impaired older adults and takes about 90 seconds to administer (75). The DSST will be conducted at BV, FU3, and FU6. The Trail Making A and B Test measures executive functioning and task-switching, is highly sensitive to change and takes 5-10 minutes to administer (76). This test will be performed at BV, FU3, and FU6. An MMSE (a mini-mental state exam) will also be performed at the BV.

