For this study, Recombinant Human lactoferrin (rhLF) a partially iron saturated form of lactoferrin in 250 mg capsules and matching placebo capsules will be provided by Ventria Bioscience Biotech company at bulk pricing. Each capsule will contain 250 mg of rhlactoferrin (rhLF) as active ingredient and cellulose, magnesium stearate, and silicon dioxide as inert ingredients. Subjects will receive either 1500 mg of rhlactoferrin in capsule form twice a day or a placebo in exact matching capsules. Dosing will be six 250 mg capsules twice a day based on prior dosing used safely in studies of diarrhea in a nursing home population (70). This treatment will take place for approximately 3 months (87 days). Recombinant human lactoferrin (rhLF) is produced through standard methods of genetic modification and plant transformation. The rice grain in which the protein accumulates is stable and well suited as a production system Recombinant human lactoferrin has been purified from transgenic rice using standard food industry procedures and current good manufacturing practices. Each placebo capsule will contain cellulose, magnesium stearate, and silicon dioxide, manufactured in full compliance with all pharmaceutical regulation.

7. Study Statistics

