Based on a two-sided two-sample t-test with a Type I error of 0.05, a sample size of 23 subjects per group (46 in total) will achieve 80% power to detect a difference of 0.86 SD or greater in logIL-6 between the treatment group and the placebo group at the end of the 6-month trial. Secondly, we will compare the linear rate of change in logIL-6 between the treatment and the placebo groups by modeling the individual trajectories of the outcome. With 20 subjects per group, three repeated measurements of IL-6 assessed at baseline, 3, and 6 months, and a correlation of 0.54 between measurements, we will have 80% power to detect a difference of 1.3 SD units (equivalent to a cross-sectional between-group difference of 0.65SD different at 6 months) or greater in the yearly rate of change in logIL-6 between the treatment and the placebo group. The within subject between-measurement correlation of 0.54 was estimated using longitudinal data from the Women's Health and Aging Study II. Therefore, using longitudinal data, we will have adequate power to detect a difference similar to the 0.63 SD (or 2.5 pg/mL) difference observed at the end of a 6-month, randomized clinical study of a ribonuclease-enriched lactoferrin supplement in post-menopausal women (16). Given these calculations, we are aiming to recruit up to 60 individuals, 30 in each group, in order to maximize our ability to detect differences between treatment and placebo groups. This increased number beyond what are calculated here will take into account anticipated drop outs during the treatment period and leave us with an estimated 'complete completer' group of 46 total. In addition, we are estimating that we will need to have at least 250 individuals recruited into the protocol in order to identify those eligible by inflammatory mediator criteria listed above.

8. Risks

Six Minute Walk Test: This is performed by having the participant walk along a straight hallway for six minutes and measuring the distance walked and the sensation of leg fatigue and dyspnea. The participant may stop at any time if they feel uncomfortable. As with any exercise test, there is a theoretical risk that a participant could suffer cardiac risk from arrhythmia or ischemia, or orthopedic risk from falling or stumbling. Risks are minimized by conducting the test in a medically supervised environment with trained personnel.

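### IL-6 and sTNFR1 are both primary, but the statistics section tests and powers only logIL-6 and gives no rule for success

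*Combined protocol and SAP*

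**What the plan says.** Section 2 (Objectives) sets the primary objective as efficacy "in reducing chronic inflammation as measured by IL-6 and sTNFR1 in the bloodstream". Section 4 (Measurements Performed at Visits) repeats the pair: "Primary outcome will be serum IL-6 and sTNFR1 as measured by ELISA".

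Section 7 (Study Statistics) is the only statistical text, and every test, effect size and power figure in it concerns logIL-6. It starts with a two-sided 0.05 two-sample t-test at the end of the 6-month trial, sized at 23 per group for 80% power to detect "0.86 SD or greater in logIL-6 between the treatment group and the placebo group". It continues: "Secondly, we will compare the linear rate of change in logIL-6 between the treatment and the placebo groups". That analysis is sized at 20 per group, with measurements at baseline, 3 and 6 months and a correlation of 0.54, for 1.3 SD per year, which the plan equates to 0.65 SD at 6 months. The section then concludes that "using longitudinal data, we will have adequate power to detect a difference similar to the 0.63 SD" reported in an earlier lactoferrin study. sTNFR1 does not appear in section 7.

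Section 3 (Background) describes "an inflammatory index (IIS) combining serum levels of IL6 and sTNFR1", but the protocol does not make that index the primary outcome.

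**The concern.** Half of the declared primary outcome has no planned analysis, and nothing defines a positive trial. The rule could be both markers, either marker, or the combined index. The same data could be called positive or negative under a rule chosen after the results are known.

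It is also not fully settled which logIL-6 analysis decides. The order of presentation and the 46 expected completers (23 per group) point to the t-test. The claim of adequate power for the effect the plan cites rests on the longitudinal analysis instead.

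The stakes are moderate. This is a pilot meant to inform a more definitive trial, but the Abstract says it will have determined whether rhLF can safely reduce measures of chronic inflammation, and section 7 fixes a formal alpha.

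**Working it through.** **Inputs from section 7.** Two-sided alpha 0.05; 23 per group; 0.86 SD; 20 per group, correlation 0.54 and 1.3 SD per year for the slope; cited effect 0.63 SD. **Assumptions, not in the documents.** Correlation between the IL-6 and sTNFR1 tests (range shown); sTNFR1 effect set equal to 0.86 SD; correlation 0.54 equal for every pair of visits.

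**1. The plan's own figure.** Noncentral t, df = 2n − 2, noncentrality d·√(n/2). With d = 0.86 and n = 23, noncentrality is 0.86 × √11.5 = 2.916 and power is 81.4%; with n = 22 it is 79.6%. The stated 23 per group reproduces.

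**2. Two readings of the two-marker objective, 23 per group.** Joint power is the chance that both t-tests reach 0.05 (simulated; at correlation 0 it is 0.814² = 0.66). The either-marker error is the bivariate normal probability that at least one |Z| exceeds 1.96 under no effect (at correlation 0, 1 − 0.95² = 0.0975).

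| Correlation | Both required: joint power | Either suffices: error rate |
|---|---|---|
| 0 | 0.66 | 0.0975 |
| 0.3 | 0.69 | 0.095 |
| 0.5 | 0.70 | 0.091 |
| 0.8 | 0.745 | 0.078 |
| 0.9 | 0.765 | 0.070 |

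If both are required, the error rate cannot exceed 0.05, but joint power is below 80% throughout the range. If sTNFR1 differed by only 0.63 SD (again an assumption), joint power would be 45% to 53% at correlations 0 to 0.7.

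**3. Two analyses of logIL-6.** Two plausible slope models are used because section 7 does not specify one.
- Unconstrained slope (the 0-to-6-month change): variance 2(1 − 0.54) = 0.92; correlation with the 6-month difference 0.46/√0.92 = 0.480. If either analysis could count, the error is 9.1%.
- Linear model with a common baseline: with x = (0, 0.5, 1) and R the 3 × 3 correlation matrix, x′R⁻¹x = 1.4475; correlation with the 6-month difference 1/√1.4475 = 0.831. The error is 7.6%.

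**4. The adequate-power sentence.**
- t-test, 0.63 SD, 23 per group: 55%.
- Slope, 20 per group, 1.3 × 0.5 = 0.65 SD at 6 months, power = Φ(δ/SE − 1.96):
  - Unconstrained: SE = √(2 × 0.92/20) = 0.303; 0.65/0.303 = 2.143; power 57%.
  - Common baseline: SE = √(2/(20 × 1.4475)) = 0.263; 0.65/0.263 = 2.473; power 70%.

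Neither model gives 80%.

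**5. Does a fixed order hold 0.05?** If logIL-6 has no effect, any false claim must first pass its 0.05 test. If logIL-6 has an effect and sTNFR1 has none, a false claim needs the sTNFR1 test to reject, again at most 0.05. Simulation under no effect on either marker gave 0.049 to 0.050. logIL-6 keeps 81.4% power; an equal split at 0.025 each would leave 72.3%.

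**The case against.** A reader might infer that the trial runs a false-positive rate near 10%. The document does not support that. Sections 2 and 4 join the markers with *and*, and section 7 presents the slope comparison second. On the plainest reading both markers are needed and 0.05 already holds. This objection stands: the inflation figures are conditional, and the firm part of the point is the missing sTNFR1 analysis, success rule and joint power.

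A reader might also take the fixed order as a cure for power. It is not. Claiming both markers still needs both tests significant, so power for that claim is unchanged.

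The order itself is open to challenge. Section 5 lets participants qualify on TNFR1 alone, so gating sTNFR1 behind IL-6 could leave a real effect on a primary marker unclaimable. Requiring both markers, or testing the index, would also fit the text. IL-6 goes first here only because it is the one marker with a stated effect size.

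Finally, strict error control matters less in a pilot. That limits the weight of the point but does not remove it, since the plan sets a formal alpha and an efficacy objective.

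**Conclusion.** The point holds in limited form and should be corrected. The 0.05 and 80% in section 7 describe one logIL-6 t-test and are not assured for the two-marker primary objective. If both markers are required, the gap is power: between 66% and 77%, assuming 0.86 SD on each marker and correlation 0 to 0.9. If either were allowed, the error would be about 7% to 9.75%, but no such rule is written.

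The adequate-power sentence is not supported by either slope model tried: about 57% to 70% against the stated 80%, assuming equal correlation across visits and, as in the plan, a linear divergence to 6 months. A different, unstated model could give another figure.

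A reader might also conclude that 6 months is the wrong time point. The documents do not show that. They show only that treatment lasts about 87 days (section 6), so the 6-month draw falls roughly 183 − 87 = 96 days after the last capsule, while IL-6 is also measured at 3 months. The sponsor should confirm the choice.

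**What to change.** In section 7, before unblinding:

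1. Name one deciding analysis and one time point. The default is the 6-month logIL-6 comparison already powered; the sponsor confirms or replaces the time point.
2. Test logIL-6 at two-sided 0.05. Test log sTNFR1 by the same analysis and time point at two-sided 0.05 only if logIL-6 is significant. Label the other logIL-6 analysis supportive.
3. If the sponsor means that both markers must succeed, say so instead; no alpha adjustment is then needed. If the combined index is meant, one test of it also holds 0.05, but it needs its own effect size and power.
4. State that 80% power covers logIL-6 only, and that power to claim both markers is lower, with the range and assumptions above.
5. Restate the adequate-power sentence with the t-test figure (55% for 0.63 SD) and the slope figure (about 57% to 70% for 0.65 SD), naming the slope model.

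The cost is a few sentences, with no added participants or blood draws. Moving the deciding test to 3 months would keep 81.4% power only if the SD-unit effect and the number per arm were the same; the documents give no 3-month effect. The main downside of the fixed order is that sTNFR1 cannot be claimed alone.

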Side Effect Assessment: A Side Effect Assessment will be conducted at FU1, FU2, and FU3. The purpose of this assessment is to monitor participants' responses to lactoferrin and to assess for any adverse side effects.

Activity Assessment: Participants will answer questions about their physical activity and energy levels. This assessment is conducted at BV, FU3, and FU6.

Frailty Assessment: This assessment is completed at BV, FU3, and FU6. This assessment measures participants' walking speed and grip strength, and includes questions about weight loss.

Vital Signs: Participants' vital signs will be measured at every study visit. These measurements include height, weight, blood pressure, respiratory rate, and temperature.

Additional Physical and Functional Measurements:

Home Mobility Measurement: An Acti-Graph® Link Activity monitor will be placed on the participant's non-dominant wrist at the end of the BV. This model includes an ambient light designed to provide environmental information and a gyroscope and magnetometer to capture position and rotational data. Accelerometry counts will be measured at a sampling frequency of 80 hertz for 7 days immediately

after completing the BV, 3-month, and 6-month visits. Participants will be asked to wear the device at all times except when swimming for >30 minutes. Monitors will be mailed via pre-addressed express mail packets where all raw data will be downloaded using commercial software (ACTLIFE, v6) to derive activity data in g force and counts/min. The JHU Statistical Methods for Applications and Research in Technology ("SMART"-stats) group, developers of the "movelets" technology that enables the use of raw data (62), will use collected data to: (i) characterize cumulative daily activity, (ii) assess daily circadian patterns of activity, (iii) assess physical activity variability, (iv) model patterns of daily activity, and (iv) estimate walking speed (62, 63, 64). These measurements greatly extend what is normally available from accelerometers and will complement mobility measures by describing function enacted in daily life.

5. Inclusion/Exclusion Criteria

Inclusion: Age 70 and older; able to complete 4- meter timed walk; walking speed ≤ 1.0 m/sec; serum IL-6 level ≥ 2.5 pg/ml or TNFR1 level ≥ 1500 pg/ml. Consistent with NIH guidelines, both genders and minority persons are enrolled. Participants will be followed for 6 months to investigate the effects of the treatments on gait speed and other outcomes.

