Exclusion criteria: Participants with IL-6 levels above 30.0 pg /ul. Daily anti-inflammatory drug use (prednisone, Advil, Aleve, Remicade, Enbrel, methotrexate, standing NSAID, aspirin greater than 325 mg per day), lower extremity mobility disability caused by Parkinson's disease, CVA with residual motor deficit, severe osteo or rheumatoid arthritis, symptomatic claudication, hospitalization within 3 months for MI, angina, infection requiring antibiotics, or joint replacement, and for other reasons that markers may be elevated such as active or chronic malignancies MMSE < 21.

6. Drugs/ Substances/ Devices

Lactoferrin is a basic glycoprotein initially identified in milk but subsequently identified in most exocrine secretions and in granules secreted from neutrophils (8). It has pleiotropic anti-inflammatory effects that range from the coating and degradation of invading organisms and their antigenic cellular components, to the sequestration of free iron needed by invading organisms to thrive, to the suppression of inflammatory (NFkB) signaling, and the modulation of the adaptive immune system (8-10;12). A recent study that characterized a lactoferrin knock out mouse demonstrated a colonic inflammatory phenotype which suggests an important role for lactoferrin at the interface between the colon and the immune system (11). Given the evidence for altered immunogenic intestinal flora in frail older adults, and the decreasing barrier function of the aging intestinal epithelium, and the known anti-inflammatory functions of lactoferrin, the use of oral lactoferrin for CI suppression in older adults is highly biologically plausible. (13-15;65-68). Beyond this mechanistic rationale, oral lactoferrin has demonstrated to safely and significantly reduce the incidence of neonatal sepsis in prior studies (69) and post-antibiotic diarrhea in older nursing facility residents (70). In older adults, lactoferrin was well tolerated in late stage cancer patients and increased overall survival in a study that did not include inflammatory measures (71, 72). A prior study of bovine lactoferrin demonstrated significant reductions of CRP and IL-6 levels in post-menopausal women treated for 6 months with minimal or no side effects (16). Lactoferrin has previously been used as a chronic diarrhea intervention in other vulnerable populations with minimal safety concerns and few if any adverse outcomes related to lactoferrin (70;73,74).

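### Entry guards against transient IL-6 elevation but the outcome draws do not, and one large spike at 6 months can move the unadjusted t-test on 23 per arm

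*Combined protocol and SAP*

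**What the plan says.** **Outcome.** Section 4 (Measurements Performed at Visits, Phlebotomy): "Primary outcome will be serum IL-6 and sTNFR1 as measured by ELISA". Blood is drawn at SV, ABT, BV, FU1, FU3 and FU6, with one draw per visit.

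**Entry.** Section 4 (Screening Visit) requires a raised cytokine to be confirmed on a second draw within four weeks. Section 5 excludes hospitalisation in the previous 3 months for a list of causes that includes "infection requiring antibiotics, or joint replacement, and for other reasons that markers may be elevated". It also sets an IL-6 ceiling of 30.0 pg/ul, against an inclusion floor of 2.5 pg/ml.

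**Information available at follow-up.** Section 4 says "vital signs will be measured at every study visit", and these include temperature. A short history review takes place at BV and every follow-up visit. A CBC with differential accompanies the cytokine draws, and study physicians review laboratory results. The stated uses are eligibility, safety and covariates.

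**Analysis.** Section 7 plans a "two-sided two-sample t-test with a Type I error of 0.05" and states that "a sample size of 23 subjects per group (46 in total) will achieve 80% power". The detectable effect is given as 0.86 SD on the logIL-6 scale, and the arms are compared "at the end of the 6-month trial". A second analysis compares linear rates of change using baseline, 3 and 6 months, with a between-measurement correlation of 0.54.

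No section says to postpone or repeat a cytokine draw during acute illness, to mark such a sample, or to treat it differently in the analysis.

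**The concern.** The trial is about chronic low-grade inflammation, and the plan does not accept one raised value as proof of it at entry. The same analyte is then the outcome, measured once per visit in people aged 70 or over during six months of follow-up, when some intercurrent illness is foreseeable. A t-test compares means, so with 23 per arm one extreme value shifts its arm's mean by 1/23 of the spike and inflates the pooled variance.

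Two things are at stake. One participant's illness on one day could weigh heavily on whether a true effect is detected. And if such a value appears, any decision about it made after unblinding would be a post-hoc choice about which primary-outcome values count.

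**Working it through.** **1. Inputs.** From Section 7: two-sided alpha 0.05, 23 per arm, difference 0.86 SD on logIL-6 at 6 months, correlation 0.54. Not in the documents, so assumed: the SD of logIL-6, the spike size (1 to 5 SD) and the chance of a spike. The planning SD is taken as free of spikes.

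**2. The plan's own figure.** Noncentrality = 0.86 × √(23/2) = 2.92 on 44 df. Power is 81.4%, and 79.6% at 22 per arm, so 23 per arm for 80% reproduces.

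**3. One spike at FU6.** Adding k SD to one of 23 values moves that arm's mean by k/23 and raises its variance by about k²(1/23)(22/23). For k = 3 in the active arm:
- difference = 0.86 − 3/23 = 0.73
- pooled variance = 1 + 9 × 0.0416/2 = 1.187, so SD = 1.09
- standardised difference = 0.73/1.09 = 0.67, giving power of about 60%

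Simulation (200,000 trials) gives:

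| Spike | Active arm | Placebo arm | Average | Average loss from 81.4% |
|---|---|---|---|---|
| 1 SD | 76.8% | 84.6% | 80.7% | 0.7 points |
| 2 SD | 69.8% | 86.2% | 78.0% | 3.4 points |
| 3 SD | 60.8% | 87.1% | 73.9% | 7.5 points |
| 4 SD | 50.2% | 87.5% | 68.8% | 12.6 points |
| 5 SD | 38.1% | 87.0% | 62.6% | 18.8 points |

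An active-arm spike narrows the expected difference; a placebo-arm spike widens it. With spikes falling at random in both arms and no true effect, the rejection rate is 0.047-0.050.

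**4. What a spike of k SD means.** k = ln(fold rise)/(SD of ln IL-6). For an assumed SD of 0.5 to 1.0, a 3-fold rise is 1.10/0.5 = 2.2 down to 1.10/1.0 = 1.1 SD. A 10-fold rise is 2.30/0.5 = 4.6 down to 2.3 SD.

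**5. The entry ceiling.** As printed, 30.0 pg/ul is 30,000 pg/ml, or 12,000 times the floor, and would exclude almost no one. Read per ml it would be 12 times the floor: ln 12 = 2.48, or 3.1-5.0 SD for an assumed SD of 0.8-0.5. The two units must be reconciled.

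**6. Which visits matter.** Only FU6 enters the t-test. BV, 3-month and 6-month values enter the rate-of-change analysis. For three equally spaced complete visits the least-squares slope is (6-month − baseline)/6, so the 3-month value acts mainly through residual variance. FU1 enters neither analysis. I give no power figure for the slope analysis because its model is not specified.

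**7. The alternative analysis.** Adjusting for baseline with r = 0.54 gives 0.86/√(1 − 0.54²) = 0.86/0.842 = 1.02 residual SD; noncentrality 1.02 × 3.39 = 3.46 on 43 df; power about 92%. Simulation (40,000 trials, 23 per arm, each FU6 sample having an assumed 4% chance of a spike, so 46 × 0.04 = 1.8 expected):

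| Spike | t-test | ANCOVA | Rank-based ANCOVA |
|---|---|---|---|
| none | 81% | 92% | 90% |
| 1 SD | 80% | 90% | 88% |
| 2 SD | 76% | 86% | 85% |
| 3 SD | 70% | 78% | 82% |
| 4 SD | 63% | 70% | 82% |
| 5 SD | 56% | 62% | 81% |

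With the same 4% chance at BV as well, rank-based ANCOVA has 79-81% for 3-5 SD. Baseline adjustment gives the gain when samples are clean; ranks give the protection when spikes are large.

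**The case against.** **The power loss depends on what the planning SD contains.** Section 7 does not say that its SD excludes sick-day samples. If 0.86 SD refers to the SD of values as observed, spikes included, simulated t-test power stays at about 81% for 3-5 SD spikes at a 4% rate. This stands, and the loss is therefore only an illustration.

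**Spike size and frequency are assumed.** This also stands. At 1-2 SD the average loss is only about 1-3 points. A reader might infer that any infection at any follow-up visit costs 7-19 points. The documents do not support that: the range is an average over arms for one 3-5 SD spike at FU6, and a placebo-arm spike raises power.

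**Entry does not clearly screen out acute illness.** The infection item sits in a list that begins with hospitalisation, so a minor outpatient infection is not clearly excluded, and the ceiling's units are unresolved. It is fair to say only that entry guards against transient elevation, chiefly through the repeat draw.

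**The data for an illness check already exist.** True of history, temperature and CBC, but no rule links them to the cytokine value. Building that link after the results are known is what should be avoided.

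**A rank test may not help.** An unadjusted rank test has about 79% power with no spikes and loses to the t-test at 1-2 SD, so it is only a trade-off. The baseline-adjusted version beats the unadjusted t-test in every row of the second table above.

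**Infection-driven IL-6 may be part of the effect.** Sections 1 and 6 describe anti-infective actions of lactoferrin. This is a sound reason not to drop such values from the main comparison.

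**Conclusion.** The gap is real: transient elevation is guarded against at entry and left unaddressed at the outcome draws, and the one named test is sensitive to a single extreme value at 23 per arm. Its size is conditional. With a spike-free planning SD, one FU6 spike of 2-5 SD lowers average power from 81% to between 78% and 63%. For 3-5 SD the result is 61-38% or about 87%, depending on the arm.

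The t-test is not invalid, because Type I error holds. Nor do the documents show that the trial will lose this power, since they give no log SD, spike size or illness rate. The figures cover logIL-6 only, not sTNFR1. The advantage of baseline adjustment rests on the plan's correlation of 0.54, which comes from an observational cohort and could be lower in participants selected for raised cytokines.

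**What to change.** 1. **BV.** Reschedule the draw when the history review or temperature already taken shows acute illness. The investigators should set the window in advance.
2. **FU1, FU3 and FU6.** Draw as scheduled. Flag the sample, blind to arm and cytokine result, from the history review, temperature and CBC with differential already collected.
3. **Main 6-month comparison.** Keep all randomised participants and all values. Replace the unadjusted t-test with one prespecified baseline-adjusted analysis of logIL-6, either bounded-influence or rank-based. The simulated figures here are for rank-based ANCOVA only.
4. **Supportive analysis.** Repeat the comparison with flagged samples set to missing. It must stay supportive: rhLF may itself prevent infections, so removing those samples could remove part of the effect or unbalance the arms.
5. **Ceiling.** Reconcile the units of the IL-6 ceiling and floor in Section 5.

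The cost is one form field, some analysis-plan wording, an occasional delayed BV, and about 2-3 points of power against ordinary ANCOVA if no spikes occur. Against the planned t-test, power with no spikes rises from 81% to about 90%.
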